*Conceptual Framework.* We predict the Partnership intervention will improve school culture so that staff and students are more knowledgeable about mental health, less concerned about stigma, and more proactive in identifying students in need and connecting them to more intensive Tier 2 or Tier 3 services; more students/families receive Tier 2 and 3 services and receive them in a more timely manner; students and families are more invested in services, empowered to influence treatment directions, experience greater therapeutic alliance with SBH staff, and receive a higher dose of evidence-based services; and, impacts of evidence-based services are amplified based on greater knowledge of mental health. These factors will be associated with better performance on measures of social, EB, and academic functioning than students in the Wellness Group alone.

*Engagement Plan.* The engagement plan has been informed by lessons learned from the recent PCORI Eugene Washington Engagement award, and reviewer feedback from the prior application. The SAB has actively guided our work and this resubmission, with some members providing input since 2015, and new members (i.e., educators, additional family members, payers) added based on PCORI guidance. The SAB has 13 members in SC and 10 in MD (23 total) and includes: patients/caregivers (some of whom are end users at study schools), educators, mental health/community partners, public and private funders, and community partners (see Tables 3 and 4 in Appendix for a full listing of members by site). Please note that the SAB is representative of study sites in relation to racial/ethnic/cultural background of students. The SAB will collaborate at multiple levels, as a full 23-member board, within SC and MD, and in three subgroups of patients/caregivers, educators, and mental health/community partners. The SAB subgroups will convene in bi-monthly conference calls for one hour to provide input and feedback in all three domains of the PCORI engagement rubric: Planning, Conduct and Dissemination. Each SAB member will be compensated \$50 per hour for their time spent on the calls, as well as the time they spend reviewing materials offline (estimated at 6 hours annually). Additionally, the SAB will meet in person once annually, to engage in more comprehensive discussion of

PRINCIPAL INVESTIGATOR: [name]

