**Analytic Plan.** The proposed project is a cluster-randomized controlled trial (J=22 schools; 11 per treatment arm) comparing the efficacy of Wellness vs. Partnership services. As a general analytic plan, we will use hierarchical linear modeling (HLM) to evaluate the project aims. Specifically, we will use two-level HLM models to account for students being nested within schools. Though one might conceptualize this proposal as a three-level model (i.e., students nested within schools, and schools nested within sites), it would be neither feasible nor recommended to model site as a multilevel variable given there are only two sites in the design (56). In line with best practice, we will integrate site (i.e., SC vs. MD) as a covariate in the statistical models to contain any potential effects of this variable. Based on prior research conducted by the team, we expect intraclass correlations (ICCs) to warrant the incorporation of random intercepts to account for violations of independence. We will also test independence assumptions for the treatment parameters to determine how sensitive treatment effects are to potential violations of independence, and will include random slopes to account for nested treatment effects if ICCs exceed .01. For transparency, we will report both fixed and random effects (i.e. intercepts and slopes) of the model. Additionally, we will iteratively subset the model using a k-1 sensitivity analysis to determine the influence of individual sites on parameter estimates. We will estimate statistical models using full information maximum likelihood to accommodate any missing data (57). We will use maximum likelihood with robust standard errors to estimate models that include the Zero Inflated Poisson link function for count

PRINCIPAL INVESTIGATOR: [name]

outcomes (e.g. absences, referrals). This general analytic framework will be used in aims 1 and 2. Details, exceptions, and modifications to it are discussed below.

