*Model modifications for students receiving tier 3 services.* To evaluate the effects of the enhanced treatment on students who receive tier 3 clinical services, and to accommodate the fact that there will be a rolling admission into clinical services, the treatment parameter will be interacted with a dosage parameter measuring each individual student's weeks of treatment received. This interaction term will provide a treatment effect estimate that is calibrated by dosage, as measured by weeks of treatment received. Because we will use an active treatment, we will be able to detect treatment-by-dosage differences between the enhanced and control treatments. To accommodate the possibility that random assignment does not create exactly equal groups with K=22, and to provide interpretable estimates of change in response to the intervention, we will use difference scores as the dependent variable unit of analysis for students receiving tier 3 clinical services. This will facilitate the direct examination of how services received over time influences youth change. The null hypothesis associated with change scores is that baseline differences remain constant and there would thus be no mean change across measurement occasions. Rogosa and colleagues (58-60) highlight the utility of using difference scores to evaluate pretest-posttest change in similar studies, indicating that previous work critical of this approach has been misleading in that it focused on several restrictive assumptions including high correlations of pretest and posttest measures as well as equal variances across measures over time. Given our previous research, outcomes, and statistical model, we believe that difference scores are the appropriate dependent variable.

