Given the experiment will examine intent-to-treat effects in a real-world setting, we will conduct analyses to investigate variability in implementation and compliance to enhance causal effect interpretation of clients "as treated." Specifically, we will use a Bayesian Additive Regression Tree approach (BART; 61) to delineate the impact of key treatment assumptions (e.g., compliance, fidelity, etc.), as well as to estimate the impact of assumption violations on the estimation of causal effects in the design. BART is an extension of Classification and Regression Tree (CART) models that is based on a recursive partitioning algorithm that explains variation in the outcome through repeated splits of the data into homogenous subgroups that are similar on predictor variables. One significant strength of BART is that it is capable of handling a large number of predictors and incorporates higher-order interactions that may be excluded from parametric analysis. Research indicates that BART is insensitive to tuning parameters and produces more accurate estimates of treatment effects compared to other methods of analyzing treatment effect heterogeneity (i.e., propensity score matching, propensity-weighted estimators, instrumental variable procedures, and regression adjustment; 61). Note that this BART enhancement to the randomized, experimental design should not be mistaken for a Bayesian trial design.

*Power considerations.* The design originally included a planned sample size of approximately N=2800 (1400 per arm) for Aims 1 and 2. We previously revised power estimates for these study aims that consider the possibility of reduced participant involvement given COVID-19 and recruitment challenges more broadly, with a revised sample size of approximately N=1400 (700 per arm). With the research study period concluding in June 2023, we have revised the enrollment projection to a conservative estimate of N=1225. With our currently active sites (J=22) and the total number of students enrolled in the study (N=1225, including expected spring 2023 enrollment), assuming 30% of variance

PRINCIPAL INVESTIGATOR: [name]

explained in the primary outcomes by pre-test covariates, and 80% power, we have a minimum detectable effect size (MDES) of .29. If we reach our goal of 1400 students, we will be at .28.

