A priori power analyses indicate that we will be adequately powered to detect any primary outcome that has an effect size of  $d=.29$  or greater (i.e., between small [ $d=.2$ ] and medium [ $d=.5$ ] in size per Cohen, 1988). Statistical software does not differentiate between one variable (e.g., depression) or another (e.g., anxiety) when executing power analysis for an outcome. Notably, Ferguson (2009) recommends that "minimum effect size representing a 'practically' significant effect for social science data" with difference measures like Cohen's  $d$  is .41.

Variation in cluster size is a typical (and expected) occurrence in cluster-randomized trials, with a priori power analyses invoking the projected average sample size per cluster for projected MDES estimates to accommodate differences in cluster size. Moreover, methodological literature has shown that any negative influence of cluster imbalance is limited to situations where there is a severe Pareto imbalance, defined as "a situation in which 80% of the subjects actually belong to only 20% of the clusters" (Guittet, Ravaud, & Giraudeau, 2006). This is not the situation here, and thus we expect the observed imbalance to have a negligible impact on analyses. Power analysis for the study corresponds to the ITT effect of the intervention, wherein the probability of the intervention's ability to reject a null-hypothesis of no intervention effect is considered. Power estimates are not provided for the dose-response effect (i.e., the effect of treatment at varying dose levels) as this will be calculated using a Bayesian method (i.e., Bayesian Additive Regression Trees, BART).

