Estimating dose-response effects using a conventional, frequentist treatment\*dosage interaction would violate the strong ignorability assumption, confound effects with varying characteristics of participants and sites, and yield biased estimates (e.g., 69,70). The BART models proposed in the current application have demonstrated efficacy in estimating treatment effects in quasi-experimental studies that may vary as a function of a continuous variable, such as treatment dose (71). The BART approach will provide an estimate of the treatment effect for those who received the intervention conditional on baseline covariates (i.e., conditional treatment effect on treated). We will calculate conditional treatment effects on treatment for each individual following the Neyman-Rubin causal model (72,73). The BART models will yield an effect size for each varying level of exposure, as well as provide a credible interval (analogous to a frequentist confidence interval) for the effect estimate. The BART models will also allow missing data to be included as a feature in the predictive model using a "missingness incorporated in attributes" approach. This means that BART will use all available data. Kapleiner and Bleich (74) demonstrated that this approach is computationally efficient and that results are comparable to other advanced missing data approaches (e.g., multiple imputation).

We will conduct additional analyses to ensure the results from our original models are not due to random noise in the sample. Specifically, we will conduct 250 Monte Carlo simulations in which a random binomial variable will be generated to represent an instrumental variable such that it will be uncorrelated with covariates or outcomes. Then we will regress each of the outcomes on the binomial variable yielding a parameter representing the relationship between the instrumental and binomial variable that is unrelated to the outcomes. This analysis will test the sensitivity of our BART models on estimated treatment effects and determine how robust our credible intervals are.

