There are essentially six classes of student participants, with groups based on grade level at the start of the intervention vs. comparison (IvC) period of the study, which begins in the 2019-20 school year. There is a four-year IvC period, 2019-20, 2020-21, 2021-22, and 2022-23. Group A will be in the 6th grade in 2019-20, with students experiencing 1-3 years of services in this time interval. These students could have received services in 6th, 7th and/or 8th grades during the IvC period. Group B will be in the 7th grade in 2019-20, with students experiencing 1-2 years of services in this time interval. These students could have received services in 7th and/or 8th grades during the IvC period. Group C will be in the 8th grade in 2019-20, with students experiencing 1 year of services in this time interval. Group D will enter the study in 6th grade in 2020-21. Group E will enter the study in 6th grade in 2021-22. Group F will enter the study in 2022-2023 while in 6th grade.

*Identifying eligible participants.* Participants already receiving treatment and those newly referred for services will be eligible to participate and recruited by their SBH clinician. Throughout the implementation phase (years 1-4) each school will use their existing referral process to identify students in need of treatment which will be followed up and confirmed by the SBH clinician prior to enrolling them in the study.

*Overcoming barriers to enrollment.* In addition to our successful experiences with the opt-out procedure to be used for stream 1 data collection, both mental health centers have participated in extensive and similar research with the investigators leading this study. The SAB will provide input on the development of consent materials, and methods of communication, making sure that they are appealing. The process of utilizing e-consent will be convenient and streamlined for Tier 3 participants. Additionally, participant incentives are proposed, in the amount of \$20 per parent assessment battery, and a token of appreciation for each student assessment battery to incentivize participation.

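### Tier 3 outcomes: the .29 MDES credits pre-test covariates with 30% of variance, but the written difference-score model names no intake covariate, so .29 is not shown to apply to it

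*Combined protocol and SAP*

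**What the plan says.** Under Model modifications for students receiving tier 3 services, the outcome is set as follows: "we will use difference scores as the dependent variable unit of analysis for students receiving tier 3 clinical services". One reason given is "To accommodate the possibility that random assignment does not create exactly equal groups with K=22". No intake score or other pre-test covariate is named there.

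The general Analytic Plan names one adjustment covariate for the multilevel models: "we will integrate site (i.e., SC vs. MD) as a covariate in the statistical models".

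Power considerations takes 22 schools, N=1225 and 30% of variance "explained in the primary outcomes by pre-test covariates, and 80% power, we have a minimum detectable effect size (MDES) of .29". It gives .28 at N=1400 and applies .29 to any primary outcome. It adds: "Power analysis for the study corresponds to the ITT effect of the intervention".

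Baseline covariates do appear further on in that section, but for the BART models, which give "an estimate of the treatment effect for those who received the intervention conditional on baseline covariates". The human-subjects text (Inclusion of Women and Minorities, Inclusion of Children) promises in general terms that analyses will account for participant characteristics. It names no model and no variable.

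**The concern.** The 30% credit belongs to a model that contains pre-test covariates. The Tier 3 model as written contains the pre-test only through subtraction, and subtraction removes 30% of variance only under particular correlations or SD ratios. The documents give no ICC, no alpha, no pre-post correlation and no level (student, school or both) for the 30%. A reader therefore cannot tell whether the Brief Problem Checklist and CASAFS comparisons have 80% power at .29 or clearly less.

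A second matter follows from the plan's own reason for differencing, which is possible chance imbalance with 22 schools. Differencing deals with that only in part; adjustment for intake deals with it fully.

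The point concerns the simple intent-to-treat contrast that the power statement covers. It does not concern the treatment-by-weeks interaction, for which the plan gives no power.

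**Working it through.** **Inputs.** From the Analytic Plan and Power considerations: J=22 (11 per arm), N=1225 (1225/22 = 55.7 per school), 80% power, 30% of variance, MDES .29. Assumed: two-sided alpha .05, 20 df, a follow-up score for all 1,225, results in follow-up SD units.

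**Formula.** SE² = (4/22)[ICC×B + (1−ICC)×W/55.7], where B and W are the remaining fractions of school-level and student-level variance. MDES = 2.945×SE (noncentral t, 20 df).

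**Reproducing .29.** It needs an ICC, so I solved for one.
- 30% at both levels (B=W=.70): ICC .059.
- 30% at student level only (B=1, W=.70): ICC .041.

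Both give .286 at N=1400, just above the rounding point for the plan's .28. Slightly lower ICCs (.056 to .058, or .039 to .041) match both stated figures, and the change is immaterial below.

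**Adjusting against subtracting.** With equal SDs and correlation r, adjustment leaves 1−r² of the variance and differencing leaves 2(1−r). At r=√.30=.548 these are .70 and .905, so differencing removes about 10%, not 30%.

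**Case 1: same r at both levels, ICC .059.**

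| r | MDES, plain difference | MDES, intake added |
|---|---|---|
| .40 | .38 | .32 |
| .50 | .35 | .30 |
| .55 | .33 | .29 |
| .60 | .31 | .28 |
| .65 | .29 | .26 |
| .70 | .27 | .25 |

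At r=.55 the plain difference score has 69% power at d=.29 and 94% at d=.41, the practical-significance value that Power considerations cites. If intake SD is k times follow-up SD, the remaining variance is 1+k²−2rk; at r=.55, k=.8 gives .30 and k=1.2 gives .37.

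**Case 2: 30% at student level only, ICC .041, W=.905, B=2(1−school r).**

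| School-level r | MDES, plain difference | Power at .29 | MDES, student intake added |
|---|---|---|---|
| 0 | .39 | 54% | .32 |
| .30 | .34 | 67% | .29 |
| .55 | .29 | 80% | .25 |
| .70 | .25 | 90% | .23 |

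The plain score meets .29 from a school-level r of about .54. At the worst entry (.39), power at d=.41 is 83%.

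**Chance imbalance.** The unadjusted estimate is off by (1−r) times the intake difference: .452×.2 = .09 SD for a .2 SD difference. The chance difference has SD √[(4/22)(.0593+.9407/55.7)] = .118, so it exceeds .1 SD in about 39% of trials and .2 SD in 8 to 9%. A simulation randomizing within state, with site in the model and site assumed to carry half the between-school variance, gives 27% and 3%. Adjustment leaves essentially no such error.

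**Stable, referral-driven difference.** Here the ranking reverses. A stable .2 SD arm difference with no treatment effect shifts the adjusted estimate by .09 SD and the unadjusted one by 0.

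**The case against.** The strongest reply is that the plan chose difference scores on purpose and may be right to. Students enter Tier 3 after schools are randomized: "Participants already receiving treatment and those newly referred for services will be eligible to participate and recruited by their SBH clinician". The Conceptual Framework predicts that Partnership staff will be "more proactive in identifying students in need and connecting them to more intensive Tier 2 or Tier 3 services". A referral-driven intake difference is thus close to the trial's own hypothesis. If it is stable and the arms would otherwise change in parallel, the difference score is the valid estimator. With a stable .2 SD difference and the case 1 standard errors (.098 adjusted, .112 unadjusted), root mean squared error is √(.098²+.09²) = .133 adjusted against .112 unadjusted, and the adjusted test rejects a true null about 14% of the time. The unadjusted estimator has the lower error once the stable difference passes about .12 SD. This stands, and it is why both estimates must be shown.

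It can also be said that silence is not exclusion: the power text speaks of pre-test covariates, and nothing forbids them in the Tier 3 model. That is fair, but then the covariates need naming.

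Two stronger readings are tempting. A reader might infer that .29 is wrong or that the trial is underpowered. The documents do not support that, because differencing itself uses the intake score and meets .29 at plausible correlations. A reader might also infer that difference scores are an invalid outcome. They are not, and the stated rationale does not conflict with an intake covariate.

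**Conclusion.** The mismatch is real: .29 rests on a variance credit that the written Tier 3 model is not shown to earn. Whether there is a shortfall cannot be settled from the documents. At r=.55 at both levels with equal SDs, the MDES is about .33 with 69% power at d=.29. At r of about .65 it is .29. If the 30% applies at student level only, it lies between about .25 and .39 for school-level correlations from .7 down to 0. All of this assumes two-sided alpha .05, ICCs back-solved from .29, and complete follow-up.

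Severity is minor to moderate, because power at d=.41 stays at about 83% or more in these scenarios. The case for adding intake is a precision gain (about .33 to .29 in case 1) and removal of chance-imbalance error, against a possible bias if referral shifts intake stably.

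**What to change.** In the Tier 3 model section, state that for the Brief Problem Checklist and CASAFS the linear model includes the student's intake score on the same measure. The difference score can stay as the dependent variable: with intake in a linear model, the treatment estimate equals that from the follow-up score. Limit the sentence to these two measures. The CSQ-8 is collected only at three months or closure, so it has no intake value, and the equivalence does not carry over to the Zero Inflated Poisson counts.

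Report the unadjusted difference-score estimate beside the adjusted one, and intake scores by arm. At r=.55 the two estimates differ by about .45 times the intake difference, so showing both shows how much hangs on the choice.

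If the unadjusted difference score stays primary, restate the MDES for that analysis with its ICC, alpha, assumed pre-post correlation and the level at which the 30% applies.

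Cost: one or two sentences, no new data (intake is already collected) and one degree of freedom (.290 becomes .291). One limit: above a school-level correlation of about .83 to .86, student intake alone no longer beats the plain difference score. The school-mean intake score would then be needed as well (.292 on the same basis); otherwise it is optional.

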complete the survey, which assesses the dimensions of engagement, safety, and environment once annually at the end of each academic year for the four years of intervention vs. comparison (2019-20, 2020-21, 2021-22, 2022-23). Due to the COVID-19 pandemic, the team was unable to collect SCS data from students in [REDACTED] schools during the first academic year (2019-2020). While this means a compromised set of Year 1 data on school climate for the [REDACTED] site, such measurement is intact for SC, and we will still be able to document trends in time in school climate in [REDACTED] for years 2-4 of the intervention vs. comparison period. Additionally, the study team will collect rosters of classrooms receiving The Guide Curriculum (GC). This will enable two sets of analyses: first, we will document which students receiving Tier 3 services and participating fully in the study are exposed to GC and account for this in terms of interventions received in analyses. Second, this will significantly expand a second level of enrollment for the study, as we will have de-identified academic records for all students (related to recently approved amendments), and will explore impacts of the GC on academic record variables (e.g., discipline problems, grades, attendance) for students in classrooms in Partnership schools receiving it compared to students in demographically comparable classrooms from Wellness schools that do not receive it.

The second stream of data collection will focus on students receiving Tier 3 services and consenting to be in the study. Clinicians will collect these measures with students and families at intake, every three months, and at case closure, using an electronic data portal coordinated by [name] and the Informatics Team at the Medical University of South Carolina (MUSC). The measurement strategy for each of the study aims is presented here:

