*Study retention.* Due to documented accessibility advantages of SBH (16) and our past experiences, Tier 3 students and parents are likely to remain involved in the study throughout the span of treatment. Additionally, the intervention requires no extra effort to participate outside of the assessments, with similar types of assessments routinely used in treatment for progress monitoring. In similar studies conducted, the most common reason for study attrition was due to students transferring to another school, which has been nominal across school wide populations. However, Tier 3 students experiencing EB problems are more likely to transfer schools than the general population.

*Incorporating research activities into routine care.* All research activities will be included in routine SBH functions. Consent to participate will be integrated into the existing process that clinicians use to obtain consent for treatment. Students and their parents may notice that their clinician is utilizing some new strategies, however all within parameters of expected clinical care. The same is true in the Partnership condition, will all enhancements those that would logically occur in a school embracing innovation and pursuing holistic strategies to remove barriers to student learning.

*Training and experience of recruitment personnel.* For students receiving Tier 3 services, the 20 clinicians will assist in study recruitment. Beginning in Year 2, a clinician was added in two [REDACTED] schools, one per condition for a total of 22 clinicians. Beginning in Year 3, two additional schools were added, one per condition, for a total of 22 schools and 24 clinicians. All clinicians will have a master's degree in a behavioral health discipline (e.g., psychology, counseling, social work) and will hold a valid license to provide psychological services or be under the supervision of a licensed clinician. Each clinician will participate in human subjects training prior to recruitment efforts and will be trained by the research team on recruitment procedures. The Lead Research Manager, [name], will oversee recruitment efforts with the PI, [name] and Co-I/MD Site PI, [name], as guided by the SAB and building on experiences from prior RCTs conducted

PRINCIPAL INVESTIGATOR: [name]

by the research team, including a large current RCT funded by the National Institute of Justice that includes an opt-out procedure. See below for recruitment parameters.

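### The stated MDES of .29 is optimistic for the Tier 3 change-score outcomes: it counts every enrolled student, assumes schools of average size and allows for no missing follow-up

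*Combined protocol and SAP*

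**What the plan says.** The Analytic Plan describes a "cluster-randomized controlled trial (J=22 schools; 11 per treatment arm". Under Power considerations the calculation uses "the total number of students enrolled in the study (N=1225, including expected spring 2023 enrollment", assumes 30% of variance "explained in the primary outcomes by pre-test covariates, and 80% power", and concludes: "we have a minimum detectable effect size (MDES) of .29. If we reach our goal of 1400 students, we will be at .28". The next paragraph generalises this, calling the trial "adequately powered to detect any primary outcome that has an effect size of" d=.29 or more.

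On unequal schools, the same section says the calculation uses the projected average number per school. It argues that imbalance does harm only when 80% of subjects sit in 20% of clusters, says this is not the case here, and concludes: "we expect the observed imbalance to have a negligible impact on analyses".

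Other sections bear on the number analysable:

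- The Tier 3 modifications make difference scores the dependent variable.
- The measurement plan says: "Clinicians will collect these measures with students and families at intake, every three months, and at case closure".
- The study period ends in June 2023, and the recruitment table projects the last enrolment on 6/30/2023.
- Study retention expects Tier 3 families to stay involved during treatment, but adds that "Tier 3 students experiencing EB problems are more likely to transfer schools than the general population". It gives no rate.
- Missing data are to be handled by full information maximum likelihood (FIML).

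**The concern.** A difference score exists only for a student who has a second measurement. A student enrolled in May or June 2023 counts towards 1225 but, unless the case closes before the study ends, contributes no change score. FIML does not help much, because the whole outcome is missing rather than part of it. Transfers act in the same direction.

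The argument on imbalance is also too strong. Precision falls as soon as school sizes vary, not only at an 80/20 split. Some variation is built in: under Training and experience of recruitment personnel, two schools joined only in Year 3 and two others gained a second clinician in Year 2.

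Each omission makes .29 look better than the analysable data would support, and the plan then applies .29 to any primary outcome. A null Tier 3 result would be read against a threshold that is somewhat too favourable.

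**Working it through.** **Inputs from the plan.** J=22 schools, 11 per arm; N=1225 (1225/22 = 55.7 per school) or 1400; 30% of variance explained; 80% power.

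**Not stated, so assumed.** Two-sided alpha of .05. The 30% applies either at both levels or at student level only. The ICC is solved from the plan's own figures. The ICC of .01 in the Analytic Plan is a threshold for adding random slopes, not a planning value.

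**Formula.** With 20 df, t(.975) + t(.80) = 2.086 + 0.860 = 2.946, and

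MDES = 2.946 × √[ ICC(1−R²school)/(J/4) + (1−ICC)(1−R²student)/(N/4) ].

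Power at d=.29 comes from the noncentral t.

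**Reproducing .29 and .28.** Take ICC = .0587 and R²=.30 at both levels.

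- N=1225: .0587×.7/5.5 = .00747 and .9413×.7/306.25 = .00215. The sum is .00962, so MDES = 2.946 × .0981 = .289.
- N=1400: the student term becomes .9413×.7/350 = .00188, so MDES = .285, on the edge of rounding to .28.

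The lower limit, at which N=1225 gives .285, is ICC = .0566. Both printed figures therefore hold together only for an ICC of about .056-.059 (R² at both levels) or .039-.041 (student level only). The unrounded starting MDES is then .285-.289. An exact .290 would give .286 at N=1400, which rounds to .29, not .28.

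**Late enrolment.** The plan gives 35 a month (Recruitment Plan), 42 (recruitment table) and 39 (its footnote); 1225/36 = 34. Three months at 34-42 is 102-126 students, or 8-10% of 1225, leaving 1123-1099.

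**Unequal schools.** School i carries information wᵢ = 1/[ICC(1−R²school) + (1−ICC)(1−R²student)/nᵢ], and the variance is 4/Σwᵢ. Sizes were simulated from a gamma distribution with the CV shown.

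**Results**, for ICC .0566 to .0587 (the student-level-only band agrees to within .001 in MDES and 0.2 points of power):

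| Scenario | MDES | Power at .29 |
|---|---|---|
| As stated | .285-.289 | 81-80% |
| 8-10% loss, equal schools | .288-.293 | 81-79% |
| 20% loss, equal schools | .293-.297 | 79-78% |
| No loss, CV .4 | .289-.293 | 80-79% |
| No loss, CV .6 | .295-.299 | 79-78% |
| 10% loss, CV .6 | .299-.303 | 78-76% |
| 20% loss, CV .6 | .304-.308 | 76-75% |

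**A hand check of the 80/20 rule.** Suppose 7 of the 22 schools (32%) hold 60% of students: 105 each, against 32.7 in the other 15 (CV .61). At ICC .0587, w = 1/(.0411+.0063) = 21.1 and 1/(.0411+.0202) = 16.3. Then Σw = 7×21.1 + 15×16.3 = 392, and MDES = 2.946 × √(4/392) = .297. Power is 78%, against 80.3% for equal schools. An 80/20 split (4 schools holding 80%) has a CV of about 1.6, so precision is lost well short of it.

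**For scale.** At N=1225 with equal schools and R² at both levels, MDES is .204 at ICC .02 and .327 at ICC .08. The undisclosed ICC matters more than either omission.

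**The case against.** A reader might infer that the design fails to deliver 80% power at .29. The documents do not support that. They state no ICC, alpha, attrition rate or school-size CV for this calculation. At the low end of the implied ICC band, 10% loss with equal schools still leaves 80.4%, and CV .4 with no loss leaves 80.2%. The only loss that can be tied to the plan's dates is the 8-10%, and the Recruitment Plan expects faster enrolment at the start, so the last months may hold fewer students than the average implies. No arithmetic error is shown either, since one ICC reproduces both printed figures.

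Nor do all spring 2023 enrollees lack follow-up: those enrolled from January to March can reach three months by June, and case closure is also an assessment point. Session counts need no post-intake questionnaire, and the school-wide records do not rest on the 1225.

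The plan does discuss imbalance, and its wording suggests that school counts had been seen. The only CV that can be built from the text is small: two schools with half the exposure of the other 20 give .15. Every MDES above is also below the .41 that the plan cites as practically significant, so that comparison survives.

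All of this stands and limits the size of the point. It does not justify counting students who cannot have a change score, the blanket claim for any primary outcome, or the 80/20 rule.

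**Conclusion.** The point holds in a modest form: .29 is optimistic for the Tier 3 difference-score outcomes and cannot be verified as written. Late enrolment alone costs about one point of power. Moderate imbalance (CV .6) costs between two and three points. With 20% loss as well, the MDES is about .30-.31 and power at d=.29 about 75-76%. The loss of 20% and the CV of .6 are assumptions. The calculation also rests on two-sided alpha .05 and on the ICC implied by the pair .29/.28.

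The Aim 1 session counts and Aim 2a records are not affected by missing post scores. The Aim 1 satisfaction score is collected at three months or case closure, so it does need a post-intake contact. One figure for every primary outcome is therefore not appropriate.

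**What to change.** In Power considerations:

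1. State the ICC, the alpha and its sidedness, and the level at which the 30% of variance applies.
2. Recompute the MDES for each outcome, using the expected number of students with a post-intake score where one is needed, and the observed school-size CV.
3. Replace the single .29 for any primary outcome with those figures.
4. Delete the statement that imbalance matters only in the 80/20 case, and report the school-size distribution instead.

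The cost is a short recalculation from counts that the study team should already hold, and probably a slightly less favourable figure for the Tier 3 outcomes. No extra enrolment or design change is needed.
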